7.2.3 Registration

This is performed per Section 4.2. Patients should be treated within 28 days of registration.

7.2.4 All Cycles, Days 1-28

Day 1 examinations marked * do not need to be repeated if already performed within +/-3 days prior to Day 1. Examinations marked ** may be performed within +/- 2 days.

- **Medical history:** Day 1*
- **Physical examination:** Day 1. Height, weight, body surface area and description of external signs of cancer. To be performed by an authorized investigator or nurse.
- **ECOG performance status:** Day 1.
- **Vital signs:** Days 1, 2, 3 and 4. Only on Cycle 1 perform also on day 19** . Heart rate, blood pressure, respiratory rate and temperature.
- **Hematology:** Cycle 1 performed on Days 1*, 4** and 19** (repeat to follow up on AEs as appropriate). Subsequent cycles perform only on Day 1* . Hemoglobin, hematocrit, mean corpuscular volume, platelet count, WBC and WBC differentials.
- **Coagulation:** Day 1* INR and APTT. If patient is receiving warfarin, assessments should be done weekly.
- **Blood chemistry:** Cycle 1 perform on Days 1* and 4** (repeat to follow up on AEs as appropriate). Subsequent cycles perform only on Day 1* . Sodium, potassium, calcium, magnesium, chloride, glucose, creatinine, total bilirubin, AST, ALT, urea, total protein, albumin and LDH, direct bilirubin and uric acid.
- **CA-125:** Day 1* .
- **Urinalysis:** Day 1* . Dipstick for protein, glucose, bilirubin and blood (perform microscopy if more than one positive dipstick test).
- **LVEF:** Assessed by echocardiography within 7 days prior to Cycle 3 and Cycle 6 and every 3rd cycle thereafter. LVEF is mandatory before each additional administration of PLD that exceeds a lifetime cumulative anthracycline dose of 450 mg/m².
- **Tumor biopsy:** Cycle 1 only (optional). Tumor biopsy performed optimally at the end of APR-246 infusion on Day 3 of the first cycle, however a biopsy obtained at the end of the

APR-246 infusion on Day 2 is acceptable. Refer to Laboratory Manual for detailed instructions.

- **Exploratory biomarkers:** Blood samples taken before infusion of APR-246 on Day 1 of Cycles 1, 2 and 6. The plasma samples will be collected in order to analyze circulating tumor DNA. Refer to Laboratory Manual for detailed instructions.
- **APR-246 administration:** Days 1, 2, 3 and 4.
- **PLD chemotherapy administration:** Day 4.
- **AEs:** Even though premedicated, patients should be closely monitored for hypersensitivity reactions, especially during the first cycle.
- **Concomitant medications.**
- **Tumor assessments:** CT scan/MRI at the end of Cycle 2 (within 4 days prior to the start of Cycle 3), at the end of Cycle 4 (within 4 days prior to the start of Cycle 5) and at the end of every two cycles of treatment thereafter. In patients who have discontinued therapy without progressive disease CT/MRI scans should be performed every 8 weeks until radiological progression.
- **ECG in selected patients:** Only at centers provided with Mortara ELI 150RX 12 lead ECG Recorder. 12-lead ECG, taken in triplicate:
 - Cycle 1 Day 1
 - Cycle 1, Day 4, optional, rhythm strip performed using limb leads of the 12-lead ECG machine, after the end of APR-246 infusion
 - Cycle 1 Day 19**
 - From Cycle 2 onwards performed on Day 1* each cycle

All recordings must be reviewed, dated and signed by the Investigator or an authorized subinvestigator. Refer to Laboratory Manual for detailed instructions.

- **12-lead continuous ECG Holter† in selected patients:** Only at centers provided with H12+ Holter Recorder. Cycle 1 only. Recorded for 24 hours, start prior to APR-246 administration on Day 1 and Day 4. Refer to Laboratory Manual for detailed instructions.
- **Pharmacokinetics:** At centers provided with H12+ Holter Recorder and Mortara ELI 150RX 12 lead ECG Recorder. Sampling for APR-246 in Cycle 1 on Day 1, 2, 4 and 5 (see Table 8); then sparse sampling for APR-246 on Day 1 and Day 4 from Cycle 2 onwards (see Table 9).†
- **Pharmacokinetics:** In all other patients: sparse sampling for APR-246 on Day 1 and Day 4 of all cycles (see Table 9).

† These assessments will be discontinued once sufficient evaluable data has been collected.

7.2.5 End of Treatment Visit

The end of treatment visit should take place 30 days (+/- 2 days) after the last APR-246 dose.

- **Tumor assessment:** CT scan/MRI. Tumor assessment should be performed at end of

treatment.

- **Physical examination:** Height, weight, body surface area and description of external signs of cancer. To be performed by an authorized investigator or nurse.
- **ECOG performance status.**
- **CA-125.**
- **ECG:** Standard 12-lead ECG, taken in triplicate (use Mortara ELI 150RX 12 lead ECG Recorder if provided).
- **Exploratory biomarkers:** Blood sample to analyze circulating tumor DNA. Refer to Laboratory Manual for detailed instructions.

7.2.6 Follow-up Visits

Follow-up visits should be performed at least every 8 weeks after the End of Treatment visit.

- **Tumor assessment:** CA-125 assessment and CT/MRI scans should be performed every 8 weeks until disease progression.
- **Exploratory biomarkers:** Blood samples taken at each visit before progression and at progression to analyze circulating tumor DNA. Refer to Laboratory Manual for detailed instructions.

7.2.7 After Progression

Survival after progression will be monitored every 6 months until death. This can be done remotely (e.g., via telephone, via general practitioner or via review of medical records).

7.3 Adverse Events

7.3.1 Definition of Adverse Events

An AE is the development of an undesirable medical condition or the deterioration of a pre-existing medical condition following or during exposure to a pharmaceutical product, whether or not considered causally related to the product. An undesirable medical condition can be symptoms (e.g., nausea, chest pain), signs (e.g., tachycardia, enlarged liver) or the abnormal results of an investigation (e.g., laboratory findings, ECG). In clinical studies, an AE can include an undesirable medical condition occurring at any time, including run-in or washout periods, even if no study treatment has been administered.

Any deterioration of the disease under study and associated symptoms or findings should not be regarded as an AE as far as the deterioration can be anticipated (see Section 7.3.4.8).

The term AE is used generally to include any AE whether serious or non-serious.

7.3.2 Definitions of Serious Adverse Events

A serious adverse event (SAE) is an AE occurring during any study phase (i.e., run-in, treatment, washout, follow-up) that fulfills one or more of the following criteria:

- Results in death
- Is immediately life-threatening (i.e., the patient was at risk of death at the time of the event; it does not refer to an event which hypothetically might have caused death if it was more severe)
- Requires in-patient hospitalization or prolongation of existing hospitalization
- Results in persistent or significant disability/incapacity or substantial disruption of the ability to conduct normal life functions
- Is or results in a congenital abnormality or birth defect
- Is an important medical event (may not be immediately life-threatening or result in death or hospitalization) that may jeopardize the patient or may require medical intervention to prevent one of the outcomes listed above.

For further guidance on the definition of a SAE, see Section 7.3.4.10 below and Appendix IV.

7.3.3 SAE Exceptions

The following scenarios that may lead to hospitalization should not be considered SAEs:

- Routine treatment or monitoring of the disease under study, including hospitalization due to trial related procedures (e.g. APR-246 administration) not associated with any deterioration of the patient's status;
- Elective treatment (planned before signing Informed Consent) for a pre-existing condition that is unrelated to the disease under study and has not worsened since signing Informed Consent;
- Treatment on an emergency outpatient basis for an event not fulfilling any of the definitions for an SAE;
- Social reasons, respite care in the absence of a medical condition

7.3.4 Recording of Adverse Events

7.3.4.1 Time Period for Collection of Adverse Events

AEs will be collected throughout the study, from informed consent until 30 days after the last administration of study treatment.

SAEs occurring in this period should be reported to the Theradex[®] Safety Desk in the usual manner (see Section 7.3.5).

7.3.4.2 Follow-up of Unresolved Adverse Events

All AEs should be followed until they are resolved or until the EOT visit, whichever comes first. All AEs that are still ongoing after the EOT visit, should be followed on a regular basis, according to the investigator's clinical judgment, until the event has resolved or until the investigator assesses it as chronic and all queries have been resolved. After the EOT visit, AEs that are unrelated to APR-246 (serious or non-serious) or related but not serious, do not require further recording in the eCRF. For Related SAEs that resolve, the date the event resolved and the outcome of Resolved or Resolved with sequelae, as appropriate, should be recorded on the eCRF and the SAE Report Form. The Sponsor retains the right to request additional information for any patient with ongoing AE(s) at the end of the study, if judged necessary.

If an Investigator learns of any SAEs, including death, at any time following 30 days after the last administration of study treatment and he/she considers there is a reasonable possibility that the SAE is related to the study treatment, the Investigator should notify Theradex[®] Safety Desk.

7.3.4.3 Variables

The following variables will be collected for each AE:

- AE diagnosis/description
- The date the AE started and stopped
- CTCAE version 4.0 grade
- Whether the AE is serious or not and the reason(s) it is serious
- Investigator causality rating against the investigational product (yes or no)
- Action taken with regard to study treatment
- Outcome.

For SAEs, other variables will be collected including treatment given for the event.

It is important to distinguish between serious and severe AEs. Severity is a measure of intensity whereas seriousness is defined by the criteria in Section 7.3.2. An AE of severe intensity need not necessarily be considered serious. For example, nausea that persists for several hours may be considered severe nausea, but not a SAE. On the other hand, a stroke that results in only a limited degree of disability may be considered a mild stroke but would be a SAE.

The grading scales found in the current National Cancer Institute CTCAE version 4.0 will be utilized for all events with an assigned CTCAE grading. For those events without assigned CTCAE grades, the recommendation in the CTCAE criteria that converts mild, moderate and severe events into CTCAE grades should be used. A copy of the current CTCAE version can be downloaded from the Cancer Therapy Evaluation Program web site (<http://ctep.cancer.gov>).

7.3.4.4 Causality Collection

The Investigator will assess causal relationship between investigational product and each AE, and answer ‘yes’ or ‘no’ to the question: ‘Do you consider that there is a reasonable possibility that the event may have been caused by the study treatment?’

For SAEs, causal relationship will also be assessed for other medications and study procedure(s). Note that for SAEs that could be associated with any study procedure the causal relationship is implied as ‘yes’.

A guide to the interpretation of the causality question is found in Appendix IV.

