2.4 Investigational Medicinal Product

The investigational medicinal product (IMP), APR-246 concentrate for solution for infusion 150 mg/mL, contains APR-246, 2-(hydroxymethyl)-2-(methoxymethyl)-1-azabicyclo [2,2,2] octan-3-one, is also called PRIMA-1^{Met} in the literature, where PRIMA is an acronym for p53 reactivation and induction of massive apoptosis (see IB).

The APR-246 compound has a molecular weight of 199.24 g/mol, is a racemic mixture and is isolated as a white powder. The structure of APR-246 can be seen in Figure 1 below.

Figure 1. Structure of APR-246

The IMP should be stored at 2-8°C. The IMP is a concentrated solution which should be diluted with sterile 0.9% sodium chloride solution for infusion before administration. The solution for infusion should be prepared with the prescribed dosage for each patient in accordance with the protocol and separate technical instruction. After preparation of the ready-to-use solution for infusion, the pH of the solution will range from slightly above 4 up to approximately 4.8, depending on dosage. The infusion will be slightly hypertonic. The prepared APR-246 study product is to be stored at not more than 25°C. The infusion to the patient should be finalized within 24 hours from the time of preparation.

APR-246 is a prodrug that is converted to the active compound MQ, responsible for the anticancer effects of APR-246. APR-246 in physiological conditions is converted to MQ, which has been

shown to bind to cysteines in mutant unfolded p53, stabilising the protein in a functional wild type conformation.

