6.5.2 Sub-Study APR-246 Dose Reductions

After an adverse event considered as related, the infusion time may be extended to a total of 4 hours to achieve a reduced maximum blood concentration of APR-246. If a related adverse event occurs with the 4 hour infusion, APR-246 dose will be de-escalated. Dose reductions are defined in Table 2. If there is a further need for a patient to have another dose reduction, this should be discussed with the Sponsor prior to any treatment decisions. The type, severity and duration of the symptoms, adverse event and infusion timings (start and stop) should be carefully documented in the patient’s medical charts as per trial procedures.

Table 2. Dose Modifications of APR-246 in Sub-Study

Dose Modification	APR-246 Dose and Regimen
Starting Regimen, 3-hour infusion	APR-246 4.5 g 2.3 g (for first 45 minutes) + 2.2 g (for 2 hours 15minutes)
4-hour infusion	APR-246 4.5 g 2.0 g (for first 45 minutes) + 2.5 (for 3 hours 15 minutes)
4-hour infusion of reduced amount*	APR-246 3.7 g 1.6 g (for first 45 minutes) + 2.1 g (for 3 hours 15 minutes)

* Discuss with Sponsor and or medical monitor before implementing this reduction.

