9.3 Analysis Populations

The following populations will apply:

Safety Evaluable Population: All patients who received study medication (APR-246 or PLD) will be considered evaluable for safety regardless of the duration of treatment. This population will be used

to summarize all safety parameters.

Efficacy Evaluable Population: All patients with pretreatment measurable disease by RECIST 1.1 who have at least one radiographic assessment after pretreatment or discontinue study medication early due to disease progression and have a p53 mutation will be considered evaluable for efficacy. The efficacy-evaluable population will be the primary analysis population for efficacy.

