9.4.2 Safety Data

Adverse Event Data

Safety data will be summarized for the safety evaluable population. These data will include AEs and laboratory parameters. AE terms will be coded using the Medical Dictionary for Drug Regulatory Activities (MedDRA; version 16.0 or higher). AEs will be summarized by body system, preferred term, severity and relationship to treatment. SAEs, deaths and AEs leading to early discontinuation of study drug will be summarized. DLTs will be provided in a separate listing by dose. Laboratory parameters will be summarized by maximum NCI CTCAE severity grade and also by change from study entry to scheduled time points using descriptive statistics. Laboratory parameter listings will

include the normal ranges for each parameter. Each value will be classified as falling above, below or within the normal range.

Data summaries will include only treatment-emergent AEs (TEAEs), defined as events occurring on or after Day 1 Cycle 1 up to and including 30 days after last dose.

Pharmacokinetic versus ECG Parameters

The relationship between changes in ECG parameters and plasma concentration of APR-246 will be explored where possible using non-linear mixed effects modelling.

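### The causality rating is stored against APR-246 but the question behind it asks about study treatment, and non-serious adverse events carry no PLD rating

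*Combined protocol and SAP*

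**What the plan says.** Section 7.3.4.3 lists the variables for each adverse event. One of them is "Investigator causality rating against the investigational product (yes or no"). Section 2.4 identifies that product: "The investigational medicinal product (IMP), APR-246 concentrate for solution for infusion 150 mg/mL, contains APR-246". PLD is listed separately in Section 4.4.2 as the reference product.

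Section 7.3.4.4 opens in line with that field: "The Investigator will assess causal relationship between investigational product and each AE". The question it then gives the investigator names something else: "Do you consider that there is a reasonable possibility that the event may have been caused by the study treatment". A further assessment is added for serious events only: "For SAEs, causal relationship will also be assessed for other medications and study procedure(s"). The section sends the reader to Appendix IV for guidance.

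The rating feeds the safety tables of Section 9.4.2: "AEs will be summarized by body system, preferred term, severity and relationship to treatment". No drug is named there. The safety population in Section 9.3 covers both drugs: "All patients who received study medication (APR-246 or PLD) will be considered evaluable for safety".

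**The concern.** One yes/no field has two possible objects. If an investigator reads the question as covering both infusions, a yes prompted by PLD goes into a field labelled for APR-246. If the investigator reads it as APR-246 alone, a PLD toxicity may be scored no, and nothing records that PLD was the suspected cause. For a non-serious event there is no second field to settle which reading was used.

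The design makes this matter. There is no PLD-alone arm, so investigator attribution is the main means of separating the toxicity of the two drugs. Section 3.2 makes the safety profile of the shorter APR-246 infusion, given with PLD, a primary endpoint of the Sub-Study. Section 6.5.3 deals with typical PLD events through the PLD product information and allows APR-246 alone, under conditions, when adverse events stop PLD. The protocol therefore expects drug-level attribution but lists no PLD rating for non-serious events.

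**Working it through.** No figure is stated on this point and none can be recomputed, so the check compares the passages.

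**1. What the rating is about, by place**

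| Place | Object of the causality judgement |
|---|---|
| 7.3.4.3, variable list | investigational product |
| 7.3.4.4, instruction | investigational product |
| 7.3.4.4, question | study treatment |
| 7.3.4.2, recording after the end-of-treatment visit | APR-246 |
| 7.3.4.2, late SAE notification | study treatment |
| Appendix IV, guide to the question | IMP |
| 9.4.2, tables | treatment, drug not named |

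**2. What *study treatment* means.** There is no formal definition. For both drugs: Section 5.4 says it is outlined in Section 6.0, which covers APR-246 and PLD, and Section 6.5.2.1 treats the two as one cycle. Section 9.3 defines *study medication* as either drug, but that is a related term and not the same one. For APR-246 alone: Section 5.3 speaks of study treatment with APR-246. The question in 7.3.4.4 carries no such qualifier, so the two-drug reading is the more natural one, but it is not settled.

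**3. Whether Appendix IV settles it.** It asks about the IMP, lists other drugs as an alternative explanation, and allows no where another cause is more likely. It also lets one factor, such as time course, support a yes, and it resolves ambiguous cases to related.

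**4. One event, three routes.** Take a non-serious event typical of PLD, arising after both drugs have been given:

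- *Study treatment* read as both drugs: the answer is yes, and it is stored as an APR-246 rating.
- Read as APR-246, with the alternative-cause rule applied: the answer is no, and the suspected role of PLD is not recorded.
- Read as APR-246, with the single-factor or ambiguity rule applied: the answer is yes.

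Each route can be defended from the text, and the stored value does not show which was taken.

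**5. Whether PLD attribution is captured elsewhere.** Causality for other medications is asked only for SAEs, and PLD is not named there. If PLD counts as study treatment, it is arguably not an *other* medication, so capture is uncertain even for SAEs. Section 9.2 defers detail to an SAP, which can refine tables but cannot supply a rating that was not collected.

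**6. Where the field is not used.** The response-rate test in Section 9.1 does not use causality. The DLT list in Section 6.4.1 has no general attribution requirement (only its dosing-delay item mentions toxicity as the reason), so the gate of 0 or 1 of 6 patients does not depend on this rating.

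**The case against.** The strongest reply is that 7.3.4.4 should be read whole. Its instruction names the investigational product, and the appendix it cites asks about the IMP and points to other drugs as an alternative cause. A careful investigator can score a typical PLD event as no. The safety endpoints concern the combination, and the tables in 9.4.2 are by relationship to treatment, so a combined rating may be all that was wanted. Separate ratings will often both be yes.

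Much of this stands, and it rules out several stronger readings that a reader might infer:

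- **That a site must answer yes to a PLD toxicity, or that such toxicity is always stored as APR-246-related.** Appendix IV permits no. The text supports only that it can happen.
- **That APR-246-related rates are overstated.** The routes above can push the stored answer either way, and 9.4.2 does not claim to tabulate relation to APR-246.
- **That exposure timing measures the error.** Only Days 1 to 3 of Cycle 1 precede the first on-study PLD dose: 3 of 28 days, or 3 of 10 × 28 = 280 over ten cycles. These are calendar days, not events. Timing is one of several factors in Appendix IV; APR-246 is infused without PLD on Days 1 to 3 of every cycle; and 6.5.3 allows APR-246 alone.
- **That the field drives APR-246 dose changes.** Section 6.5.2 says "After an adverse event considered as related, the infusion time may be extended to a total of 4 hours", and 6.5.1 is similarly unqualified. Both sit under 6.5, which specifies relation to APR-246, and nothing links the adverse-event form to those decisions.

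The reply does not remove the mismatch between field and question, the split guidance within Appendix IV, or the missing PLD rating. If a combined rating was intended, the label in 7.3.4.3 is wrong.

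**Conclusion.** The inconsistency is real and should be corrected; it is cheap to do so. Section 7.3.4.3 and the instruction in 7.3.4.4 rate APR-246, while the question asks about an undefined term that most naturally includes PLD. PLD toxicity can therefore be recorded as APR-246-related, sites can differ, and for non-serious events the collected rating cannot separate the drugs.

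The size cannot be stated: the documents give no basis for the share of events misattributed. The effect is confined to the relationship tables in 9.4.2 and to interpretation of the safety profile, above all in the Sub-Study, where safety is a primary objective. The efficacy conclusion and the DLT gate are untouched.

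This rests on two assumptions: that the eCRF follows 7.3.4.3 and has no PLD causality field beyond what the protocol lists, and that sites see the question as worded in 7.3.4.4.

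**What to change.** - Define *study treatment* once, and name the drug consistently in Sections 7.3.4.2 to 7.3.4.4, Appendix IV and Section 9.4.2.
- Replace the single rating with two yes/no ratings for every adverse event, serious or not: reasonable possibility of causation by APR-246, and reasonable possibility of causation by PLD.
- In Section 9.4.2, tabulate events as related to APR-246, related to PLD, and related to either. The last keeps the combination view.
- Have the sponsor reconcile the unqualified *related* in 6.5.1 and 6.5.2 with the wording of 6.5. No dosing rule is proposed here.

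The cost is one extra eCRF field and extra table columns, with no added visit or procedure. Investigators will often answer yes to both, which limits the gain, but events attributed to one drug only become visible. This should be done as early as possible, because a PLD rating not collected at the time cannot be reliably reconstructed later.
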